6.2.1 Management of stomatitis/oral mucositis/mouth ulcers

Adverse Drug Reaction	Severity	Everolimus Dose Adjustment and Management Recommendations
Stomatitis	Grade 1	No dose adjustment required. Manage with non-alcoholic or salt water (0.9%) mouth wash severaltimes a day.
	Grade 2	Temporary dose interruption until recovery to grade ≤ 1 . Re-initiate everolimus at same dose. If stomatitis recurs at grade 2, interrupt dose until recovery to grade ≤ 1 . Re-initiate everolimus at lower dose. Manage with topical analgesic mouth treatments (e.g. benzocaine, butyl aminobenzoate, tetracaine hydrochloride, methol or phenol) with or without topical corticosteroids (i.e. triamcinolone oral paste)*.
	Grade 3	Temporary dose interruption until recovery to grade ≤ 1 . Re-initiate everolimus at lower dose. Manage with topical analgesic mouth treatments (i.e. benzocaine, butyl aminobenzoate, tetracaine hydrochloride, methol or phenol) with or without topical corticosteroids (i.e. triamcinolone oral paste)*
	Grade 4	Discontinue everolimus and treat with appropriate medical therapy.

* using agents containing hydrogen peroxide, iodine, and thyme derivatives in management of stomatitis as they may worsen mouth ulcers.

Stomatitis/oral mucositis/mouth ulcers due to everolimus should be treated using local supportive care. Investigators in earlier trials have described the oral toxicities associated with everolimus as mouth ulcers, rather than mucositis or stomatitis. If the examination reveals mouth ulcers rather than a more general inflammation of the mouth, the adverse event should be classified as mouth ulcers. Please follow the paradigm below for treatment of stomatitis/oral mucositis/mouth ulcers:

1. For mild toxicity (Grade 1), use conservative measures such as **non-alcoholic mouth wash or salt water (0.9%) mouth wash** several times a day until resolution.
2. For more severe toxicity (Grade 2 in which case patients have pain but are able to maintain adequate oral alimentation, or Grade 3 in which case patients cannot maintain adequate oral alimentation), the suggested treatments are **topical analgesic mouth treatments (i.e., local anesthetics such as benzocaine, butyl aminobenzoate, tetracaine hydrochloride, menthol, or phenol)** with or without **topical corticosteroids**, such as triamcinolone oral paste 0.1% (Kenalog in Orabase®).

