3. Agents containing hydrogen peroxide, iodine, and thyme derivatives may tend to worsen mouth ulcers. It is preferable to avoid these agents.
4. Antifungal agents must be avoided unless a fungal infection is diagnosed. In particular, systemic imidazole antifungal agents (ketoconazole, fluconazole, itraconazole, etc.) should be avoided in all patients due to their strong inhibition of everolimus metabolism, thereby leading to higher everolimus exposures. Therefore, topical

antifungal agents are preferred if an infection is diagnosed. Similarly, antiviral agents such as acyclovir should be avoided unless a viral infection is diagnosed.

Note: Stomatitis/oral mucositis should be appropriately graded using the functional grading given on the NCI-CTC for adverse events, CTCAE v 4.0. Dose reductions are made according to section 6.3.1 (Non-hematological toxicity) and Section 6.3.3.

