6.3 Dose Modifications/Delays

6.3.1 General dose modification/Delays

Dose modifications for toxicities not otherwise covered in section 6.2 are listed in the table below. Patients who do not recover to grade 2 or less toxicity within 28 days will be removed from protocol therapy except where noted (ie. pneumonitis). In addition, patients may hold study intervention (pazopanib and everolimus) for greater than 28 days if the patient's physician and the overall principal investigator, [name], agree that the patient is deriving clinical benefit from the study drugs. Dose modifications for specific toxicities are covered in sections 6.2 and 6.3.

All toxicities, both during the DLT period and after it has been completed, will follow the guidelines laid out here in sections 6.2 and 6.3.

For definition of a Dose Limiting Toxicity, refer back to section 5.4.

Non-hematological toxicity

Toxicity	Actions
Non-Infectious Pneumonitis	Please refer to section 6.2.3
Reactivation of HBV or HCV flare	Please refer to section 6.2.4
Non-hematological toxicity Grade 2 (except pneumonitis – refer to section 6.2.3) (except hypertension, proteinuria, venous or arterial thrombosis, QTc prolongation- refer to section 6.3.2) (except hepatotoxicity – refer to section 6.3.3) (except elevated amylase and lipase- refer to section 6.3.5)	If the toxicity is tolerable to the patient, maintain the same dose. If the toxicity is “intolerable” to patient, interrupt pazopanib and everolimus until recovery to grade ≤ 1 . Then reintroduce pazopanib and everolimus at same dose. If event returns to “intolerable” grade 2, then interrupt pazopanib and everolimus until recovery to grade ≤ 1 . Then reintroduce pazopanib and everolimus at one dose level lower. If event is recurrent “intolerable” grade 2 despite two dose reductions, discontinue pazopanib and everolimus.
Grade 3 or 4 (except hyperlipidemia ¹) (except pneumonitis – refer to section 6.2.3) (except hypertension, proteinuria, venous or arterial thrombosis, QTc prolongation- refer to section 6.3.2) (except hepatotoxicity – refer to section 6.3.3)	Interrupt pazopanib and everolimus until recovery to grade ≤ 1 . Then reintroduce pazopanib and everolimus at one dose level lower. No more than 2 dose reductions allowed.
Stomatitis / oral mucositis / mouth ulcers	See section 6.2.3 Management of stomatitis / oral mucositis / mouth ulcers

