Recurrence of grade 3 toxicity after dose reduction	Reduce dose to the next lower dose level, if available. The lowest possible dose level of everolimus is 5 mg every other day (2.5 mg daily). Below this level, everolimus must be discontinued.
	Interrupt everolimus administration until resolution to \leq grade 1 or baseline

Intolerable grade 2 mucositis, or grade 3 AE, except hyperglycemia or hypertriglyceridemia or hypercholesterolemia (see Section 6.2.2.)	
grade / value.
 
If resolution occurs within \leq 7 days, everolimus should be re-started at the dose level prior to interruption.
 
If resolution takes $>$ 7 days, or if event recurs within 28 days, hold everolimus until recovery to \leq grade 1 or baseline grade / value and reintroduce everolimus at one dose level lower, if available.
 
Patients will be withdrawn from the study if they fail to recover to \leq grade 1 or baseline grade / value within 28 days.

Any other grade 4	
Hold everolimus until recovery to grade \leq 1 or baseline value
 
Reintroduce everolimus at one dose level lower, if available.

Grade 3 or 4 clinical liver failure (asterixis or encephalopathy/coma)	
Discontinue everolimus and Pazopanib

Recurrence of intolerable grade 2 mucositis or grade 3 event after dose reduction	
Reduce dose to the next lower dose level, if available. The lowest possible dose level of everolimus is 2.5 mg daily. Below this level, everolimus must be discontinued. If toxicity recurs at Grade 3, consider discontinuation.

Recurrence of grade 4 after dose reduction	
Discontinue everolimus and Pazopanib

Any non-hematologic toxicity requiring everolimus interruption for $>$ 28 days	
Discontinue everolimus and Pazopanib

¹Grade 3 hyperlipidemia (hypercholesterolemia and/or hypertriglyceridemia) should be managed using medical therapies without dose reduction (see Section 6.2.2).

Hematological toxicity

Grade 2 Thrombocytopenia (platelets $<75 - 50 \times 10^9/L$)	
Interrupt pazopanib and everolimus until recovery to grade \leq 1 ($\geq 75 \times 10^9/L$). Then reintroduce pazopanib and everolimus at initial dose. If thrombocytopenia again returns to grade 2, interrupt pazopanib and everolimus until recovery to grade \leq 1. Then reintroduce everolimus at one dose level lower. No more than two dose reductions are allowed.

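### Section 6 gives conflicting dose rules for grade 3 non-hematologic events, including stomatitis, and for grade 3 hyperlipidemia, so two sites can dose the same expansion patient differently and both comply

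*Combined protocol and SAP*

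**What the plan says.** Sections 6.2 and 6.3.1 state that their dose guidelines apply to all toxicities, during and after the DLT period, so they govern expansion patients. Those patients start at pazopanib 400 mg daily with everolimus 5 mg daily. Table 6 allows one reduction, to 200 mg daily with 5 mg every other day.

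**Grade 3 and 4 events.** The non-hematological table in 6.3.1 contains two relevant sets of rows.
- The row for grade 3 or 4 toxicity interrupts both drugs until grade 1 or less. "Then reintroduce pazopanib and everolimus at one dose level lower. No more than 2 dose reductions allowed"
- A later row is labelled "Intolerable grade 2 mucositis, or grade 3 AE, except hyperglycemia or hypertriglyceridemia or hypercholesterolemia (see Section 6.2.2". It interrupts everolimus only. If the event resolves within 7 days, "everolimus should be re-started at the dose level prior to interruption". If it takes longer, or recurs within 28 days, the site is to hold everolimus and then "reintroduce everolimus at one dose level lower, if available". Pazopanib is not mentioned.
- A residual row for other grade 4 events holds everolimus and restarts it one level lower, again without mentioning pazopanib.

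**Stomatitis.** The grade 3 row of 6.2.1 always lowers everolimus: "Re-initiate everolimus at lower dose. Manage with topical analgesic mouth treatments (i.e. benzocaine, butyl aminobenzoate". The scope sentence of 6.3.1 reads "Dose modifications for toxicities not otherwise covered in section 6.2 are listed in the table below", but the note closing 6.2.1 reads "Dose reductions are made according to section 6.3.1 (Non-hematological toxicity) and Section 6.3.3".

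**Hyperlipidemia.** The grade 3 row of 6.2.2 interrupts everolimus and restarts it lower. Footnote 1 to the 6.3.1 table calls for medical therapy with no dose reduction and cites 6.2.2.

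**The concern.** A dose-modification section should give one answer for one event. Here a grade 3 event with no rule of its own, such as diarrhea, falls under two rows of the same table with different actions. Two centres treat expansion patients (12.2), and each could follow the protocol as written and give a different dose.

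The difference carries forward. The both-drug row spends the expansion patient's only reduction at the first event; the everolimus-only row can leave it unused. At the next event that calls for a reduction, one reading ends the combination and the other reduces it. Safety is a stated objective of this cohort (1.3.2, 14.1), and grade 3 stomatitis is named as the main everolimus DLT (2.1.1.6).

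**Working it through.** The plan gives no figure to reproduce. The check sets the rules side by side for a patient at the expansion starting dose.

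Inputs, from Table 6: everolimus 5 mg daily, reduced to 5 mg every other day; pazopanib 400 mg daily, reduced to 200 mg daily.

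- Everolimus, full: 5 × 7 = 35 mg/week
- Everolimus, reduced: 5 × 3.5 = 17.5 mg/week
- Ratio: 17.5 / 35 = 0.5
- Pazopanib ratio: 200 / 400 = 0.5

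| Event | One rule | Other rule |
|---|---|---|
| Grade 3 (e.g. diarrhea), resolved within 7 days, no recurrence within 28 | 6.3.1 both-drug row: everolimus 17.5 mg/week, pazopanib 200 mg/day | 6.3.1 everolimus-only row: everolimus 35 mg/week, pazopanib not stated |
| Grade 3, slower recovery | Both-drug row: 17.5 mg/week and 200 mg/day | Everolimus-only row: 17.5 mg/week, pazopanib not stated |
| Grade 4, no specific rule | Both-drug row: 17.5 mg/week and 200 mg/day | Residual grade 4 row: 17.5 mg/week, pazopanib not stated |
| Grade 3 stomatitis, resolved within 7 days, no recurrence within 28 | 6.2.1: everolimus 17.5 mg/week | 6.3.1 everolimus-only row: 35 mg/week |
| First intolerable grade 2 stomatitis, more than 7 days | 6.2.1: everolimus 35 mg/week | 6.3.1 everolimus-only row: 17.5 mg/week |
| Grade 3 hyperlipidemia | 6.2.2: everolimus 17.5 mg/week | Footnote 1: 35 mg/week |

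Can the text settle these conflicts by itself?

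1. *The two grade 3 rows.* The everolimus-only row cannot be confined to mucositis, because its exception for glucose and lipid events would then have no purpose. Giving 6.2 precedence over 6.3.1 does not help, because both rows sit inside 6.3.1. The grade 3 neutropenia row writes a 7-day rule for both drugs, so the silence on pazopanib here is a gap and not a convention of the document.
2. *Stomatitis.* The scope sentence favours 6.2.1. So does the 6.3.1 stomatitis row, which prints the title of 6.2.1. But that row gives the number 6.2.3, which is pneumonitis. The note in 6.2.1 sends reductions back to 6.3.1 and to 6.3.3, which is hepatotoxicity. The everolimus-only row also names mucositis.
3. *Hyperlipidemia.* The scope sentence again favours 6.2.2. The footnote nevertheless states the opposite of the 6.2.2 grade 3 row while citing that section.

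Frequency: the phase I update in 2.3 lists grade 3 diarrhea in 11% (1 of 9, both dose levels) and no grade 3 mucositis. Two of 6 patients at 400 mg/5 mg stopped for toxicity after 2 cycles. These counts are too small to project to 29 patients.

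**The case against.** The strongest reply is that a sensible investigator can resolve most of this. For stomatitis, the scope sentence and the printed title both point to 6.2.1, and that carries weight; what remains is ambiguity from the wrong section number and the note sending reductions back. For hyperlipidemia, precedence of 6.2 picks a winner, but the footnote still misdescribes it. For the two grade 3 rows, one might suppose that the everolimus-only row is meant for events attributed to everolimus. No text limits it that way.

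A reader might infer a third contradiction from proteinuria in 6.3.2, where Step 3 leads to a second reduction although Table 6 allows one. The documents do not support that. The stop rule with Table 6 says what happens when a patient at this dose level needs more than one reduction. The two-reduction wording has its proper use at levels +1, +2 and +2A. The same answer covers the other rows that mention two reductions. A clarifying phrase would help, but this is not an error.

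A reader might also infer that spending the one reduction means all treatment ends at the next event. It ends the combination. Section 6 lets a patient with stable disease or better who cannot tolerate one agent continue on the other alone, after discussion with the overall PI, and the dose may rise to the standard monotherapy level (Table 7).

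Finally, the factor of 2 for a grade 3 event depends on resolution within 7 days and no recurrence within 28. The documents do not say how often that happens. This limits the size of the problem but does not remove the conflict.

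**Conclusion.** The conflict is real in two places: grade 3/4 non-hematologic events (with stomatitis as a special case) in 6.3.1 against itself and against 6.2.1, and grade 3 hyperlipidemia in 6.2.2 against footnote 1. It should be fixed. Its size is a twofold difference in weekly everolimus (17.5 vs 35 mg), under the timing conditions in the table for grade 3 events and stomatitis. In addition, pazopanib is 200 mg/day under one rule and left without instruction under the other, and the single permitted reduction may be spent or kept. This rests on reading Table 6 as the dose ladder for expansion patients and on the row texts as printed.

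Two stronger conclusions are not supported.
- A reader might argue from the pharmacokinetic statement in 2.3 that the choice of drug held changes everolimus exposure markedly. That statement gives +100% for AUC, but the means beside it give 335 / 238 = 1.41, or +41%, in a handful of patients compared across studies. No weight is placed on it.
- A reader might suppose that the primary analysis is compromised. No effect on the Simon design or the go/no-go decision is claimed.

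**What to change.** 1. **Keep one grade 3/4 rule for both drugs.** In 6.3.1, delete the words *or grade 3 AE* from the everolimus-only row, and delete the residual grade 4 row, so that the both-drug row governs. If the clinicians prefer the 7-day same-dose rule, write it into the both-drug row for both agents instead.
2. **Complete that row's exceptions.** Add hyperglycemia (6.2.2), stomatitis (6.2.1), amylase/lipase (6.3.4) and hemorrhage (6.3.2). The last two matter because 6.3.4 continues the same dose for asymptomatic grade 3 amylase and lipase elevation, and 6.3.2 discontinues both drugs for grade 3 or 4 bleeding. Without these exceptions the row would still conflict with both sections.
3. **Let 6.2.1 govern stomatitis.** Correct the 6.3.1 stomatitis row to cite 6.2.1. Delete the note in 6.2.1 that sends reductions to 6.3.1 and 6.3.3, and delete the intolerable grade 2 mucositis rule from 6.3.1. State in 6.2.1 what happens to pazopanib.
4. **Make footnote 1 and the 6.2.2 grade 3 row agree**, in whichever direction is intended.
5. **Optional clarification:** state in 6.3 that the number of reductions is limited to that allowed for the starting dose level, which is one for the expansion cohort. This also settles proteinuria Step 3.

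Cost: a wording amendment with IRB approval and Novartis review (13.1), plus clinical decisions on which grade 3 rule to keep and on pazopanib during stomatitis. It adds no visits, procedures or patients.

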2 nd dose reduction	400 mg PO QD	5 mg PO QOD
--------------------------------	--------------	-------------

If a patient on dose level +2 requires more than 2 dose reductions, then the patient will stop study therapy. If a patient has pneumonitis related to everolimus, then pazopanib dose level may be maintained and everolimus dose reduced or discontinued (see Table 6.2.3).

For patients on **dose level +2A** there will be 2 dose reductions allowed:

Dose Level	Pazopanib	Everolimus
Starting dose level +2A	800 mg PO QD	5 mg PO QD
1 st dose reduction	600 mg PO QD	5 mg PO QOD
2 nd dose reduction	400 mg PO QD	discontinue

If a patient on dose level +2A requires more than 2 dose reductions, then the patient will stop study therapy. If a patient has pneumonitis related to everolimus, then pazopanib dose level may be maintained and everolimus dose reduced or discontinued (see Table 6.2.3).

Phase I expansion cohort:

Individual patient dose reductions for toxicity will be determined by initial starting dose level in the Phase I expansion cohort which was dose level -1 as per results of the first phase of the study.

For patients on **dose level -1** there will be 1 dose reduction allowed:

Table 6 Dose Expansion cohort: Dose levels.

Dose Level	Pazopanib	Everolimus
Starting dose level -1	400 mg PO QD	5 mg PO QD
1 st dose reduction	200 mg PO QD	5 mg PO QOD

If a patient on dose level -1 requires more than one dose reduction, then the patient will stop study therapy. If, however, a patient is deriving benefit from one agent, as displayed by stable disease or better at restaging, and cannot tolerate the other, the patient may continue on monotherapy of the tolerated agent after discussion with the overall PI, [name]. If one agent is discontinued for toxicity, a patient may dose-increase to the standard monotherapy dose (see Table 7) of the other agent after discussion with the overall PI.

Table 7 Standard Monotherapy Dose Levels

Dose Level	Pazopanib	Everolimus
------------	-----------	------------

Dose level when other agent is discontinued due to toxicity	800 mg PO QD	10 mg PO QD
---	--------------	-------------

If a patient has pneumonitis related to everolimus, then pazopanib dose level may be maintained and everolimus dose reduced or discontinued (see Table 6.2.3).

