Grade 3 or 4 Thrombocytopenia (platelets $<50 \times 10^9/L$)	
Interrupt pazopanib and everolimus until recovery to grade \leq 1 ($\geq 75 \times 10^9/L$). Then resume pazopanib and everolimus at one dose level lower. If grade 3 or 4 thrombocytopenia recurs, discontinue pazopanib and everolimus.

Grade 1 & 2 Neutropenia (neutrophils $\geq 1 \times 10^9/L$)	
Grade 3 Neutropenia (neutrophils $<1, \geq 0.5 \times 10^9/L$)	
No modification of dose.

	
Interrupt everolimus and Pazopanib until resolution to grade ≤ 1 or baseline value
 
If AE resolution occurs ≤ 7 days, reintroduce everolimus and pazopanib at the same dose level.
 
If AE resolution occurs > 7 days (within 28 days), reintroduce everolimus and pazopanib at one dose level lower, if available. Discontinue patient from study therapy if recurrent grade 3 or greater neutropenia after two dose reductions.

Grade 4 Neutropenia (neutrophils $< 0.5 \times 10^9/L$)
	
Interrupt pazopanib and everolimus until recovery to grade ≤ 1 (neutrophils $\geq 1.5 \times 10^9/L$). Then resume pazopanib and everolimus at one lower dose level. If grade 3 or grade 4 neutropenia occurs despite two dose reductions, discontinue pazopanib and everolimus.

Grade 3 febrile neutropenia (not life-threatening)
	
Hold further pazopanib and everolimus until the ANC $\geq 1,500/\text{mm}^3$ and fever has resolved and antibiotics are discontinued. Then resume pazopanib and everolimus at one dose level lower. If febrile neutropenia recurs, discontinue pazopanib and everolimus.

Grade 4 febrile neutropenia (life-threatening)
	
Discontinue pazopanib and everolimus.

Any hematological or non-hematological toxicity requiring interruption for ≥ 4 weeks
	
Discontinue pazopanib and everolimus

6.3.2 Management of hypertension, proteinuria, hemorrhage/bleeding, venous and arterial thrombosis, QTc prolongation

AE Terms & Descriptions	Dose Modification Algorithms

Hypertension
	

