Grade 2	Step 1. If pulmonary or GI bleed (other than hemorrhoidal bleeding), discontinue pazopanib and everolimus and continue follow-up per protocol. Otherwise, interrupt pazopanib and everolimus until the AE resolved to \leq Grade 1. Step 2. Restart pazopanib and everolimus; reduce dose by one dose level and consult with study PI, monitor as clinically indicated.
Grade 3 or 4, or Recurrent \geq Grade 2 event after	Discontinue pazopanib and everolimus and continue with follow-up per protocol.

AE Terms & Descriptions	Dose Modification Algorithms
dose interruption/reduction.	
Venous Thrombosis (DVT, PE)	
Grade 2	Continue everolimus and pazopanib at the same dose
Grade 3	
Step 1. Interrupt pazopanib and everolimus.
 
Step 2. Initiate and monitor anticoagulation as clinically indicated.
 
Step 3. Resume pazopanib and everolimus with one dose reduction only if all of the following criteria are met:
 
 • The subject must have been treated with anticoagulant at the desired level of anticoagulation for at least one week. • No Grade 3 or 4 or clinically significant Grade 2, hemorrhagic events have occurred while on anticoagulation treatment. 
Subject should be monitored as clinically indicated during anticoagulation treatment and after resuming study treatment. When treating with warfarin, international normalized ratio (INR) should be monitored within three to five days after any change in pazopanib and everolimus dosing (eg, re-initiating, escalating/de-escalating, or discontinuing pazopanib and everolimus), and then at least weekly until the INR is stable. The dose of warfarin (or its derivatives) may need to be adjusted to maintain the desired level of anticoagulation

Grade 4 and/or PE	Discontinue pazopanib and everolimus and continue follow-up per protocol.
Arterial Thrombosis/Ischemia	
Any Grade	Discontinue pazopanib and everolimus and continue follow-up per protocol.
Prolongation of QTc Interval: If the QTc is prolonged, the ECG should be manually read to ensure accuracy of the reading. The values below refer to manually-read ECGs.	
QTc \geq 480 < 500 msec	Continue pazopanib and everolimus; monitor as clinically indicated.
QTc \geq 500 msec	Discontinue pazopanib and everolimus and continue follow-up per protocol.

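### After a first grade 2 platelet fall both drugs restart at the initial dose, which read literally returns an already-reduced expansion patient to the full starting dose

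*Combined protocol and SAP*

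**What the plan says.** The grade 2 thrombocytopenia row of Section 6.3.1 holds both drugs until platelets are back to at least 75 x 10^9/L and then directs: "Then reintroduce pazopanib and everolimus at initial dose". If the count falls to grade 2 again, the drugs are held again and everolimus restarts one level lower.

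Four other rows allow a restart without a reduction:

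- Intolerable grade 2 non-hematological toxicity, first event (Section 6.3.1): "Then reintroduce pazopanib and everolimus at same dose".
- Intolerable grade 2 mucositis or a grade 3 event that resolves within 7 days (Section 6.3.1): "everolimus should be re-started at the dose level prior to interruption".
- Grade 3 neutropenia that resolves within 7 days (Section 6.3.1): "reintroduce everolimus and pazopanib at the same dose level".
- Grade 2 stomatitis, first event (Section 6.2.1): "Re-initiate everolimus at same dose".

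The expansion-cohort text of Section 6 ties reductions to the "initial starting dose level in the Phase I expansion cohort which was dose level -1", which is pazopanib 400 mg daily with everolimus 5 mg daily. Table 6 then gives a single reduced level, pazopanib 200 mg daily with everolimus 5 mg every other day.

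**The concern.** The four parallel rows look back to the dose the patient was taking when treatment stopped. The platelet row names a fixed point instead. If that point is the starting level, a patient reduced earlier for some other toxicity would go back up to full dose because of a platelet fall, a new toxicity. The dose restored would be the one in use when the earlier toxicity occurred.

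What is at stake is the safety of individual patients. Section 6.1.1 warns of potentially fatal hemorrhage if severe drug-related thrombocytopenia develops on everolimus, and Section 5.5.2 notes hemorrhagic events on pazopanib. A reduction made after a bleed is one that should not be reversed by default.

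**Working it through.** The plan states no figure to reproduce. The check compares the rows and then works out the dose difference.

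**1. What the word means elsewhere.** Section 5.4.1 uses initial dose for the level at which escalation started (dose level 0). Section 6 uses initial for the expansion starting level (dose level -1). In both places it means the starting level. Nothing in the platelet row limits it to patients with no earlier reduction.

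**2. Who would be on the reduced level before a first grade 2 platelet fall.** Several rows put patients there:

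- Grade 2 bleeding outside the lung or GI tract (Section 6.3.2): "Restart pazopanib and everolimus; reduce dose by one dose level and consult with study PI, monitor as clinically indicated".
- Hypertension scenarios B and C, and 24-hour urine protein of 3 g or more (Section 6.3.2): restart one level lower.
- Grade 4 neutropenia and grade 3 febrile neutropenia (Section 6.3.1): restart one level lower.
- Grade 3 or 4 thrombocytopenia (Section 6.3.1): "Then resume pazopanib and everolimus at one dose level lower".

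**3. Restart dose under each reading, per 28-day cycle.**

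| Patient before the platelet fall | Dose before interruption | Initial dose, read literally |
|---|---|---|
| Not reduced | 400 mg QD / 5 mg QD | 400 mg QD / 5 mg QD |
| Reduced | 200 mg QD / 5 mg QOD | 400 mg QD / 5 mg QD |

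For the reduced patient:

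- Pazopanib: 200 mg x 28 = 5,600 mg against 400 mg x 28 = 11,200 mg; ratio 11,200 / 5,600 = 2.0.
- Everolimus: 5 mg x 14 doses = 70 mg against 5 mg x 28 doses = 140 mg; ratio 140 / 70 = 2.0.

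**4. How common the trigger might be.** In the Phase I update (Section 2.3), thrombocytopenia by maximum grade was 3 patients at grade 1, 1 at grade 2 and 1 at grade 3, so 5 of 9 (56%) had some. Grade 2 as the maximum was 1/9 = 11.1%, with an exact (Clopper-Pearson) 95% interval of 0.3% to 48.2%. This pools dose levels 0 and -1. It is background only: it does not measure the sequence that matters (an earlier reduction, then a first grade 2 fall), and the documents give no figure for that.

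**5. What limits the harm.** The drugs restart only after platelets recover, and a recurrence of grade 3 or 4 thrombocytopenia stops both drugs. That stop rule acts only after a second severe fall. The row sets no early recheck. From cycle 3 the expansion calendar (Section 9.2) schedules blood counts on day 1 of each cycle only, so the next scheduled count could be about four weeks after a doubled restart.

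**The case against.** The best case for leaving the row alone is that read as a whole it explains itself. It describes a sequence: a first event, then a second that leads to one level lower. In that contrast, initial most naturally means the dose before the sequence began. Section 6 is otherwise a downward ladder. The only increase it describes for expansion patients is to monotherapy dose when the other agent has been stopped for toxicity, after discussion with the overall principal investigator. Sections 5.4.1 and 14.1 also rule out dose escalation within a patient.

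Much of this stands as evidence of intent, and the benign reading may well be what the authors meant. It does not repair the instruction. The ban on escalation within a patient sits in the Phase I escalation rules; if it also governed the expansion cohort, the platelet row read literally would contradict it.

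Two narrower points also have some force. A patient reduced for grade 3 or 4 thrombocytopenia who later falls to grade 2 could be treated as a recurrence and sent to the lower-dose branch, so that example is arguable. The bleeding, hypertension, proteinuria and neutropenia routes do not depend on it. And the bleeding row requires consultation with the study PI, but that attaches to the reduced restart after the bleed, not to a later restart after a platelet fall.

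**Conclusion.** The concern holds: the row is wrong as written, at low severity. Followed literally, it doubles the daily dose of both drugs in an expansion patient who has already been reduced. It changes nothing for a patient with no earlier reduction. The conclusion rests on taking initial in the sense Sections 5.4.1 and 6 give it, and it applies only to patients at the reduced level who then have a first grade 2 platelet fall. Their number cannot be estimated from the documents. The response endpoint, the sample size and the two-stage operating characteristics are not affected.

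**What to change.** In the grade 2 thrombocytopenia row of Section 6.3.1, replace the reference to the initial dose with a restart of both drugs at the same dose level as before the interruption. This brings the row into line with its neighbours and leaves the restart unchanged for every patient not yet reduced. It costs one phrase in the next amendment, with no extra visits, tests or patients.
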